### 5.1.4. Descriptive Statistics

Data will be summarized with descriptive statistics and/or response frequencies. Descriptive statistics for continuous variables include the sample size (N), mean, standard deviation (SD), median, minimum (Min), and maximum (Max). Descriptive statistics for categorical variables include the sample size (N) and frequency (counts and percentages).

#### 5.1.5. Significance Level and Confidence Intervals

The level of significance used for all statistical tests will be 0.05, 2-sided, unless stated otherwise.

For all endpoints for which confidence intervals are calculated, the following methods of calculation apply, unless otherwise stated.

For dichotomous variables, 2-sided 95% confidence intervals for proportions will be calculated based on the normal distribution approximation.

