2.3. Benefit/Risk Assessment

Generally, the popularity of BoNT/A cosmetic treatment of GL and LCL in adults is related to its proven efficacy for reducing moderate to severe facial lines (Beer 2006); well documented safety profile (Brin 2009); and positive impact on psychological well-being and the resulting
psychosocial benefits (Finn 2003).

In some cases, botulinum toxin effect may be observed beyond the site of local injection. The symptoms may include asthenia, generalized muscle weakness, diplopia, eyelid ptosis, dysphagia, dysphonia, dysarthria, urinary incontinence, and breathing difficulties. Swallowing and breathing difficulties can be life threatening and there have been reports of death related to distant spread of toxin effects with other BoNT/A treatments for noncosmetic indications. The risk of symptoms is probably greatest in children treated for spasticity, but symptoms can also occur in adults treated for spasticity and other conditions.

Reduced blinking after BoNT/A product injection to the orbicularis muscle can lead to corneal exposure, persistent epithelial defect, and corneal ulceration with perforation. In the use of another BoNT/A product for treatment of blepharospasm, 1 case of corneal perforation in an aphakic eye requiring corneal grafting has occurred because of this effect.

[figure not shown]

CONFIDENTIAL
MT10109L

Protocol MT10109L-004 AMD 5

3. Objectives and Endpoints

^a There are no objectives associated with the efficacy endpoints in this study.

b Baseline is from the lead-in studies for all efficacy endpoints in this study.

Protocol MT10109L-004 AMD 5

4. Study Design

Overall Design 4.1. • All participants who complete studies MT10109L-001 (GL), MT10109L-002 (LCL), MT10109L-005 (GL with or without LCL), and MT10109L-006 (LCL with or without GL) will be eligible to enroll into this 24-month open-label extension study (Study MT10109L-004). Approximately 800 participants will be enrolled at approximately 44 global sites

• Participants who complete this study will have an exit visit on Day 720.

[figure not shown]

Protocol MT10109L-004 AMD 5

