6.6. Dose Modification

This protocol does not allow for alteration from the currently outlined dosing schedule.

[figure not shown]
Participants entering from the lead-in Phase 3 studies will receive open-label study intervention based on meeting retreatment criteria.

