## 5. Statistical Analyses

## 5.1. General Considerations

[figure not shown]
The proportions of participants who achieve the efficacy endpoints will be summarized with frequency tables. The 95% CI for responders will be estimated based on the observed data by intervention group and by treatment cycle. For the US FDA, efficacy analyses will be based on the ITT population.

The safety analyses will be based on the ITT population.

Statistical analyses will be performed using version 9.4 (or newer) of statistical analysis software (SAS) on a Linux operating system.

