## 5.1.1. Treatment Group and Treatment Cycles

All safety and efficacy analyses will be integrated analyses that include data from both the leadin studies and the MT10109L-004 extension study, for participants enrolled into the extension study.

A study treatment cycle is considered to start on the day of treatment with study intervention and end on the day prior to the next study intervention or on the study exit day if there are no subsequent interventions. The nomenclature used will be "treatment cycle 1", "treatment cycle 2", "treatment cycle 3", "treatment cycle 4", "treatment cycle 5", "treatment cycle 6", "treatment

cycle 7", "treatment cycle 8", "treatment cycle 9", "treatment cycle 10", "treatment cycle 11", and "treatment cycle 12" for the lead-in and extension study possible treatment regimen cycles.

Demographic and baseline characteristic, disposition, treatment-emergent adverse event (TEAE) for entire study, vital signs, and immunogenicity tables will be summarized under leadin and extension study possible treatment regimens specified in Table 5-3. It will use planned treatment in lead-in study/ planned treatment in extension study for lead-in and extension study possible treatment regimens.

In general, there will be no substitution of missing time or date. However, any partial information will be utilized to its full extent wherever sensible. For example, a medication may be classified as a prestudy medication if the partial information of the medication ending date with only month and year permits a determination that the medication ended prior to the injection date of the study intervention.

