## 5.4. Other Safety Analyses

### 5.4.1. Extent of Exposure

Participants' exposure to the study intervention will be summarized by duration of treatment exposure, number of treatment cycles, and treatment cycle interval duration.

Duration of treatment exposure will be calculated for each extension treatment regimen

based on the number of days between the date of the first injection of that treatment (F) and the date of study exit in the extension study (E). The actual calculation used will be E - F + 1. If the date of study exit is missing, the date of the last visit will be used.

Participants' exposure to study intervention will be summarized by total duration of treatment exposure

In addition, for the entire study, the number and percentage of participants receiving 1, 2, 3 up to 12 study interventions will be summarized.

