#### MT10109L-004

#### 5.4.2. Additional Safety Assessments

No laboratory or electrocardiogram (ECG) data will be collected for this study.

Urine pregnancy tests are performed prior to each treatment and at exit visit for females of childbearing potential. Participants with positive pregnancy test results will be listed by treatment regimen, including urine sample collection date, days since Day 1 treatment (of Studies MT10109L-001, -002, -005, or -006) and days since most recent treatment.

Continuous descriptive statistics include: N1 (number of participants with nonmissing values at both baseline and the specified postbaseline analysis visit), mean, SD, median, minimum, and maximum.

Categorical variables will be summarized by number and percentage of participants. The proportions of participants who achieve the efficacy endpoints will be summarized with frequency tables. The 95% confidence interval for responders will be estimated based on the observed data by intervention group and by intervention cycle.

MT10109L-004

MT10109L-004

2.625	
-	
0.0	24
-	

Medytox

38

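### Minor: the SAP's default 95% interval for proportions is the normal approximation, which fails for any descriptive efficacy responder cell that is both small and close to 0% or 100%

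*SAP*

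**What the plan says.** SAP 5.1.5 sets a default for every endpoint that gets a confidence interval: "the following methods of calculation apply, unless otherwise stated". For dichotomous variables the method is that "2-sided 95% confidence intervals for proportions will be calculated based on the normal distribution approximation". No formula is given.

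The visible use of this default is the efficacy responder summaries. SAP 5.1 says: "The 95% CI for responders will be estimated based on the observed data by intervention group and by treatment cycle". The efficacy text that follows SAP 5.4.2 repeats it: "The 95% confidence interval for responders will be estimated based on the observed data by intervention group and by intervention cycle". Neither place names a method.

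On cycles, SAP 5.1.1 says "A study treatment cycle is considered to start on the day of treatment with study intervention" and names cycles 1 to 12. SAP 5.4.1 adds that "the number and percentage of participants receiving 1, 2, 3 up to 12 study interventions will be summarized". Protocol 6.6 says that participants "will receive open-label study intervention based on meeting retreatment criteria".

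On the standing of these analyses, footnote a in Protocol Section 3 says: "There are no objectives associated with the efficacy endpoints in this study".

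**The concern.** The normal-approximation interval estimates the standard error from the observed proportion alone. As that proportion nears 0% or 100%, the estimated error shrinks towards zero. In a small cell the interval is then too short, can run past 0% or 100%, and has zero width when everyone or no one responds.

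The plan asks for these intervals cell by cell. A cycle exists only for participants who receive a further treatment, so in a fixed set of participants the number entering each successive cycle can stay level or fall, but not rise. Reaching cycle 12 takes all 3 lead-in interventions (SAP 1) and all 9 extension interventions between Day 1 and Day 690 (SAP 1.2), an average gap of at most 689/8 = 86.1 days. Late cycles split by group are therefore where small cells could plausibly appear.

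What is at stake is the accuracy of the error bars in the efficacy tables: an interval labelled 95% that covers much less often, or that prints an impossible limit.

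**Working it through.** **Inputs from the documents.** Two-sided 95% interval (SAP 5.1.5), so z = 1.95996 and z² = 3.8415; about 800 participants (SAP 2); up to 12 cycles (SAP 5.1.1). The plan gives no interval, cell size or responder rate to reproduce.

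**Assumptions.** The normal approximation is read as the Wald interval. Cell sizes of 10 to 800 and true rates of 60% to 99% are assumed and shown as a range.

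**Formulas.** With x responders out of n and p = x/n:
- Wald: p ± z√(p(1−p)/n).
- Wilson: [p + z²/(2n) ± z√(p(1−p)/n + z²/(4n²))] / (1 + z²/n).
- Exact coverage at true rate π: the sum of binomial(n, π) probabilities over every x whose interval contains π. Band means average this over 2,001 equally spaced rates.

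**Example, 19/20.**
- Wald: √(0.95 × 0.05/20) = 0.0487; × 1.96 = 0.0955; limits 85.4% and 104.6%.
- Wilson: denominator 1 + 3.8415/20 = 1.1921; centre (0.95 + 0.0960)/1.1921 = 0.8775; half-width 1.96 × √(0.002375 + 0.002401)/1.1921 = 0.1136; limits 76.4% and 99.1%.

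**Example, 10/10.** Wald: the standard error is 0, so 100% to 100%. Wilson lower limit: 10/(10 + 3.8415) = 72.2%.

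**Mean Wald coverage (%) at assumed true rates.**

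| True rate | n=10 | 20 | 30 | 50 | 75 | 100 | 200 | 800 |
|---|---|---|---|---|---|---|---|---|
| 60-80% | 89 | 92 | 93 | 94 | 94 | 94 | 95 | 95 |
| 80-90% | 78 | 89 | 90 | 92 | 93 | 94 | 94 | 95 |
| 90-95% | 53 | 78 | 88 | 89.5 | 91 | 92 | 94 | 95 |
| 95-99% | 26 | 44 | 57 | 74 | 82 | 86 | 91 | 94 |

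Wilson gives 95-96% throughout the 90-95% row. By symmetry, rates of 5-10% mirror the 90-95% row and rates of 1-5% mirror the 95-99% row.

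These are band averages, and single rates can be worse: at n=75 the lowest coverage within 90-95% is 85.3%, at a rate of about 93.7%. Much of the loss in the smallest cells comes from zero-width intervals. At n=10 and a true rate of 90%, the chance of 10/10 is 0.9¹⁰ = 34.9%, and coverage is 65.0%.

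**When a limit passes 100%.** The Wald upper limit exceeds 1 when the number of non-responders k satisfies 0 < k < z²p = 3.8415p. For k = 3 this needs 1 − 3/n > 0.781, so n of 14 or more; k = 4 never qualifies. From n=14 upwards, then, the overshoot occurs with exactly 1 to 3 non-responders. In a large cell it is cosmetic: 797/800 gives an upper limit of 100.05%.

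**Large cells.** At n=800 no limit differs between the two methods by more than 0.15 points at rates of 60-80%, or 0.23 points at 90-95%. For 560/800, Wald gives 66.8% to 73.2% and Wilson 66.7% to 73.1%.

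**The case against.** The strongest objection is that the problem is not shown to arise. About 800 participants are expected, and the visible text gives no retreatment criteria, cell sizes or responder rates. That the number per cycle cannot rise gives a direction, not a size. This stands: a reader might infer that late cycles will hold a handful of participants with near-complete response, but the documents do not say so.

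Second, the default yields to any other stated method, much of the efficacy section is redacted, and table specifications sit in a separate document (SAP 1). A reader might infer that the plan has no small-cell method. That cannot be concluded; only the visible default can be criticised, and the fix has to be conditional.

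Third, little rests on these intervals. There are no hypotheses (SAP 3), the efficacy endpoints have no objective, and N and counts are reported (SAP 5.1.4), so a 100% to 100% interval would be recognised as an artefact. This limits the impact. It does not make under-coverage visible where both limits stay inside 0-100%.

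Fourth, a limit above 100% might be taken as a defect at any cell size. The 797/800 case shows that it is trivial in large cells.

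Fifth, the Wald reading is an inference, since the Wilson interval also rests on a normal approximation. Wald is the usual meaning of the SAP's wording, but the SAP does not settle it.

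**Conclusion.** The point holds as a minor one. As the visible text stands, the default gives wrong error bars in any responder cell that is small with a rate near 0% or 100%. At true rates of 90-95%, mean coverage is below 90% up to n=50 and is 92% at n=100. At 95-99% it is still 86% at n=100 and 91% at n=200. At 60-80% the default is adequate from about n=50 (mean 93.7%).

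This rests on three assumptions: that the SAP means the Wald interval, that no redacted text or table specification overrides it, and that such cells occur.

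A reader might extend the criticism to the primary safety results. The documents do not support that: the visible safety summaries are counts, percentages and descriptive statistics with no confidence interval. No test, sample size or primary safety conclusion changes.

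**What to change.** In SAP 5.1.5, replace the normal approximation with the two-sided 95% Wilson score interval as the default for proportions, unless the redacted text or the table specifications already name another suitable method for the responder intervals. In that case a confirmation is enough.

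The cost is one SAP sentence and one SAS option; no data collection or trial procedure changes. Intervals in small extreme cells become wider: 22.7 points instead of 19.1 for 19/20, and 16.1 instead of 0 for 20/20. Wilson is not perfect: its coverage dips to about 84% very close to 0% or 100% (for example n=20 at a true rate of about 99%).

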#### MT10109L-004

#### 5.1.6. Dictionaries

The Medical Dictionary for Regulatory Activities (MedDRA Version 24.1) will be used to code AEs, medical history, and procedures. MedDRA primary system organ class (SOC), MedDRA high level term (HLT), together with the drug record number and base preferred drug name from the enhanced version of World Health Organization Drug Dictionary (WHO DDE) Global March 2021, will be used to classify all medications (ie, prior or concomitant) recorded in the study. Base preferred name is the WHO DDE drug preferred name assigned to the 11-digit code of drug record number+01+001.

#### 5.1.7. Units

Metric system units will be used; degrees Celsius for temperature, kilograms (kg) for body weight, and centimeters (cm) for height.

#### 5.1.8. Investigator Sites

The site number for Studies MT10109L-001, -002, -005, or -006 will be used for all tables and listings.

#### 5.1.9. Study Intervention

If "Was the subject injected per protocol?" ticked as yes, the dose used of each injection will follow per protocol section 6.1.2 in extension period.

### 5.2. Participant Dispositions

#### 5.2.1. Disposition and Exit Status

The analysis will be performed using the ITT populations for overall study and by treatment cycle. The lead-in and extension study possible treatment regimens will be used.

The disposition of study participants consists of a summary of the number of participants enrolled and available in the ITT populations by treatment regimen and overall.

Tabulation of the numbers and percentages of participants in each exit status category (ie, AE, pregnancy, lost to follow-up, lack of efficacy, withdrawal by subject, physician decision, death, progressive disease, protocol deviation, noncompliance with study drug, study terminated by sponsor, site terminated by sponsor and other) will be provided for each treatment regimen of each treatment cycle. Discontinued participants will be listed along with the corresponding reason(s) for early withdrawal from the study.

## 5.3. Primary Endpoints Analysis

The primary endpoints are incidence of AEs, change from baseline in vital sign parameters, and presence of binding and neutralizing antibodies for safety.

[figure not shown]

MT10109L-004

#### 5.3.1. Definition of Endpoints

#### 5.3.1.1. Adverse Events

An AE is defined as any untoward medical occurrence in a participant or clinical investigation participant administered a pharmaceutical product and that does not necessarily have a causal relationship with this treatment.

Per case report form instructions, a new AE record will be created with a new AE onset date for any AE that worsens. Therefore, TEAEs can simply be identified as those AEs with recorded onset date on or after the date of the first study intervention and within 30 days after the study exit.

An AE will be considered a treatment-emergent serious adverse event (TESAE) if it is a TEAE that additionally meets any serious adverse event (SAE) criteria.

A SAE is defined as any AE occurring at any dose that results in any of the following outcomes: death, a life-threatening AE, inpatient hospitalization or prolongation of existing hospitalization, a persistent or significant disability/incapacity, or a congenital anomaly/birth defect. Important medical events that may not result in death, be life-threatening, or require hospitalization may be considered a SAE when, based upon appropriate medical judgment, they may jeopardize the patient or subject and may require medical or surgical intervention to prevent one of the outcomes listed in this definition. All cancer AEs are considered SAEs by Allergan. Abnormal pregnancy outcomes (eg, spontaneous abortion, fetal death, stillbirth, congenital anomalies, ectopic pregnancy) or genetic abnormalities (whether leading to an elective abortion or not) are considered SAEs.

MT10109L-004

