8.3.5. Pregnancy

- Urine pregnancy testing will be conducted for women of childbearing potential prior to each study intervention and at the study exit visit. See Appendix 7 for detailed information on definition of women of childbearing potential, use of contraceptives, and pregnancy.
- To minimize the risk of pregnancy, all women of childbearing potential must agree to use a highly effective or acceptable contraception method (Appendix 7) consistently and correctly throughout the duration of the study. For participants of childbearing potential in **Germany** and **Belgium**, only highly effective contraception methods are allowed for this study.
- Women who test positive for urine pregnancy test will NOT receive further intervention and will be discontinued from the study.

Protocol MT10109L-004 AMD 5

- Women who test positive for urine pregnancy test must complete end-of-study procedures and be followed up for pregnancy outcome.
- Any termination of pregnancy will be reported, regardless of fetal status (presence or absence of anomalies) or indication for the procedure
- If a pregnancy is reported, the investigator should inform the sponsor within 24 hours of learning of the pregnancy and should follow the procedures outlined in Appendix 7.
- Abnormal pregnancy outcomes (eg, spontaneous abortion, fetal death, stillbirth, congenital anomalies, ectopic pregnancy) or genetic abnormalities (whether leading to an elective abortion or not) are considered SAEs.

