9.4.2.1. Adverse Events

_	

An adverse event that occurs more than 30 days after study exit will not be counted as a TEAE.

An adverse event will be considered a TESAE if it is a TEAE that additionally meets any SAE criteria.

The number and percentage of participants reporting TEAEs in each study intervention group will be tabulated by system organ class and preferred term and by system organ class, preferred term, and severity

The number and percentage of participants reporting treatment-related TEAEs in each study intervention group will be tabulated by system organ class and preferred term by MT10109L cycle.

If more than 1 adverse event is coded to the same preferred term for the same participant, the participant will be counted only once for that preferred term using the most severe and most related occurrence for the summarizations by severity and by relationship to MT10109L intervention.

Protocol MT10109L-004 AMD 5

Summary tables will be provided for participants with SAEs and participants with adverse events leading to discontinuation if 5 or more participants reported such events. Listings of all adverse events, SAEs, and adverse events leading to discontinuation by participant will be presented.

The definitions of an adverse event and SAE can be found in Appendix 3.

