10.7.4. Collection of Pregnancy Information

Female Participants Who Become Pregnant

- The investigator will collect pregnancy information on any female participant who becomes pregnant while participating in this study. Information will be recorded on the appropriate form and submitted to the sponsor within 24 hours of learning of a participant's pregnancy. The participant will be followed to determine the outcome of the pregnancy. The investigator will collect follow-up information on the participant and the neonate, and the information will be forwarded to the sponsor. Generally, follow-up will not be required for longer than 6 to 8 weeks beyond the estimated delivery date. Any termination of pregnancy will be reported, regardless of fetal status (presence or absence of anomalies) or indication for the procedure.
- While pregnancy itself is not considered to be an AE or SAE, any pregnancy complication will be reported as an AE or SAE. Abnormal pregnancy outcomes (eg, spontaneous abortion, fetal death, stillbirth, congenital abnormalities, ectopic pregnancy) or genetic abnormalities (whether leading to an elective abortion or not) are always considered to be an SAE and will be reported as such. Any poststudy pregnancy-related SAE considered reasonably related to the study intervention by the investigator will be reported to the

[figure not shown]
Protocol MT10109L-004 AMD 5

sponsor as described in Section 8.3.4. While the investigator is not obligated to actively seek this information in former study participants, he or she may learn of an SAE through spontaneous reporting.

[figure not shown]
• Any female participant who becomes pregnant while participating in the study will discontinue study intervention and be withdrawn from the study.

[figure not shown]
Protocol MT10109L-004 AMD 5

[figure not shown]

[figure not shown]

[figure not shown]

[figure not shown]

[figure not shown]

[figure not shown]

[figure not shown]

[figure not shown]

[figure not shown]

[figure not shown]

[figure not shown]

[figure not shown]

[figure not shown]

[figure not shown]

[figure not shown]

[figure not shown]

[figure not shown]

[figure not shown]

Protocol MT10109L-004 AMD 5

[figure not shown]

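### Forced exit at pregnancy plus a 30-day post-exit window keeps late pregnancy outcomes out of the TESAE counts, and no visible output summarises how pregnancies end

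*SAP*

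**What the plan says.** **Time window.** SAP 5.3.1.1 identifies TEAEs as AEs with "onset date on or after the date of the first study intervention and within 30 days after the study exit". Protocol 9.4.2.1 sets the same limit: "An adverse event that occurs more than 30 days after study exit will not be counted as a TEAE".

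**Link to serious events.** SAP 5.3.1.1 makes an AE a TESAE "if it is a TEAE that additionally meets any serious adverse event (SAE) criteria". An SAE outside the window is therefore not a TESAE.

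**Pregnancy outcomes as SAEs.** The same SAP section classes as SAEs: "Abnormal pregnancy outcomes (eg, spontaneous abortion, fetal death, stillbirth, congenital anomalies, ectopic pregnancy) or genetic abnormalities". Protocol 8.3.5 and 10.7.4 agree.

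**Pregnancy forces exit.** Protocol 8.3.5 states: "Women who test positive for urine pregnancy test will NOT receive further intervention and will be discontinued from the study". Protocol 7.1 adds that she completes exit procedures and is then followed for the outcome. Protocol 10.7.4 withdraws any participant who becomes pregnant.

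**Length of follow-up.** Protocol 10.7.4: "Generally, follow-up will not be required for longer than 6 to 8 weeks beyond the estimated delivery date".

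**Reporting.** SAP 5.4.2: "Participants with positive pregnancy test results will be listed by treatment regimen, including urine sample collection date". The other fields named there are days since Day 1 of the lead-in study and days since the most recent treatment. No outcome field is shown. SAP 5.2.1 tabulates pregnancy as an exit-status category.

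**The concern.** For most adverse events, study exit is unrelated to the event, and a 30-day tail is an ordinary convention. Pregnancy is different. The condition that leads to the SAE also triggers the exit that starts the clock, and the outcome may be known only months later. The plan thus names a group of SAEs, collects them to the due date and beyond, and applies a time rule that the late members of the group cannot meet.

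Long-term safety is the study's only stated objective, and AE incidence is a primary endpoint. A report with no late-pregnancy TESAEs could be read as a safety finding when the window would give that result whatever happened. A reader of the visible outputs could see that pregnancies occurred but would find no summary of how they ended.

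**Working it through.** The plan gives no figure to reproduce. The check is date arithmetic.

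**Inputs from the documents**
- TEAE window: 30 days after exit (SAP 5.3.1.1, Protocol 9.4.2.1).
- Outcome follow-up: generally no longer than 6 to 8 weeks past the estimated delivery date (Protocol 10.7.4).
- Testing: before each intervention and at exit (Protocol 8.3.5), and at a missed cycle or on suspicion (Protocol 10.7.3).
- Up to 9 interventions, the first possible at Day 1 and the last at Day 690 (SAP 1.2). With all nine, the mean gap is (690 − 1)/8 = 86 days, or 12.3 weeks.

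**Assumptions, not in the documents**
- Term is 40 weeks.
- Exit is on the day of the positive test, at gestation g of 4 to 14 weeks. The low end is a test at a missed cycle; the high end is roughly one treatment interval.
- An outcome takes as its onset the date it occurs or is found.

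**Step 1: late outcomes.** The window closes at gestation g + 30/7 weeks. Days from exit to term = (40 − g) × 7.

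| Exit at (weeks) | Window closes (weeks) | Days to term | Multiple of 30 days |
|---|---|---|---|
| 4 | 8.3 | 252 | 8.4 |
| 8 | 12.3 | 224 | 7.5 |
| 12 | 16.3 | 196 | 6.5 |
| 14 | 18.3 | 182 | 6.1 |

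A term birth falls inside the window only if exit is at 40 − 30/7 = 35.7 weeks or later. An outcome at 20 weeks falls inside only if exit is at 20 − 30/7 = 15.7 weeks or later.

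**Step 2: a gap between test and exit.** Each day's delay moves closure by one day. With a test at 5 weeks, a 14-day delay moves closure from 5 + 30/7 = 9.3 to 5 + 44/7 = 11.3 weeks. To reach a term birth, the delay would have to be 182 − 30 = 152 days (test at 14 weeks) to 252 − 30 = 222 days (test at 4 weeks).

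**Step 3: early losses.** Consider losses after exit and before 20 weeks.
- If they are spread evenly, the share inside the window is (30/7)/(20 − g): 4.29/16 = 27% at g = 4 and 4.29/6 = 71% at g = 14.
- If their frequency halves every h weeks, the share is [1 − 2^(−(30/7)/h)] / [1 − 2^(−(20 − g)/h)]. With h from 4 down to 2 weeks, it runs from 56% (g = 4, h = 4) to 88% (g = 14, h = 2).

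Losses before exit are inside the window as well.

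**Step 4: collection against counting.** Follow-up to 6 to 8 weeks past the due date ends at most (46 − 14) × 7 = 224 to (48 − 4) × 7 = 308 days after exit. Outcomes can therefore be collected for months after they can no longer be counted as treatment-emergent.

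**The case against.** A reader might infer that abnormal pregnancy outcomes almost never reach a TESAE table. The documents do not support that. Spontaneous abortion and ectopic pregnancy are named in the same SAP sentence, testing is also done at a missed cycle, and Step 3 puts a material share of early losses inside the window.

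A reader might also infer that late events survive only in the by-subject AE listing, or that the positive-test listing is the only pregnancy output. Neither holds. Protocol 9.4.2.1 promises SAE listings, and an SAE table if 5 or more participants are affected. SAP 5.3.2.1 refers to a summary of all SAEs without limiting it to TESAEs. SAP 5.2.1 counts pregnancy exits by regimen and cycle, so a pregnancy learned of without a study urine test should appear there.

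Three further objections carry weight:
- **Unseen text.** The test-to-exit interval and schedule of activities are not visible, and output specifications are in a separate document. It cannot be said that no pregnancy-outcome listing exists anywhere, only that none is visible. Step 2 shows that a short exit delay would not change the result for term outcomes.
- **Agreement on the cut-off.** Protocol and SAP share the 30-day rule, so exempting pregnancy outcomes in the SAP alone would contradict Protocol 9.4.2.1. Counting a newborn's anomaly in participant-level incidence is also debatable. Both points argue for reporting these outcomes beside the TESAE count.
- **Small consequence.** The study is descriptive, contraception is mandatory for women of childbearing potential, and outcomes are still followed and reported to the sponsor. No safety conclusion is shown to change.

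**Conclusion.** The point stands for late outcomes. Under the stated rule, abnormal pregnancy outcomes with onset more than 30 days after exit are not TESAEs. That covers essentially all late fetal deaths, stillbirths and anomalies found at birth: with exit at 4 to 12 weeks' gestation, a term outcome falls 196 to 252 days after exit (from 182 days if exit is at 14 weeks). Early losses and ectopic pregnancies are partly captured. The 27% to 88% range for early losses illustrates the assumed timing and is not a forecast.

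Late events should still be listed, but no visible output summarises pregnancy outcomes, and neither document says whether an SAE summary includes events after the window. The result rests on a 40-week term, exit soon after detection, and onset dated at the event or its discovery. The SAP states no onset convention for a congenital anomaly. The documents give no expected number of pregnancies. The matter is one of complete and interpretable reporting and does not show that the main safety results would be wrong.

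**What to change.** Keep the 30-day TEAE rule in both documents and make three changes to the SAP:

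1. In 5.3.2.1, add to the entire-study TESAE summary a separate row or footnoted count of abnormal outcomes of all pregnancies reported during the study, regardless of onset date. Kept apart from the TESAE total, it needs no onset-date rule and does not mix neonatal events into participant incidence.
2. In 5.4.2, extend the listing from positive urine tests to all reported pregnancies, giving regimen, days since last MT10109L injection and outcome from the pregnancy form.
3. In 5.3.2.1, state whether the summary of all SAEs includes events more than 30 days after exit.

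Protocol 10.7.4 already requires the outcome data, so no new collection is needed. The cost is SAP wording, one added row and one extended listing. The SAE presentation may look slightly less favourable.
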